Minimum, n (%)																																										
<LLN																																										
Normal																																										
>ULN																																										
Post-Baseline																																										
Maximum, n (%)																																										
<LLN																																										
Normal																																										
>ULN																																										

N = Number of subjects in a specific group; n = Number of subjects with data available; Percentages are based on N;

Normal: Within normal range, LLN: Lower limit of normal, ULN: Upper limit of normal.

Only subjects with baseline and at least one post-baseline value are considered.

Baseline value is defined as the last non-missing measurement prior to, or on the date/time of the first administration of study treatment. NA = not applicable.

Page X of Y

(Notes for programmer:

- generate a post-baseline Maximum Value and post-baseline Minimum Value per subject (incl. unscheduled measurements
- LLN for creatinine clearance is fixed 90 mL/min
- if ULN (eg CC) available, please display n/a
-)

Figure 3: Selected laboratory parameters over time (Box-Whisker-Plot) - Safety Set

Box-Whisker-Plots: by <Parameter> (<unit>), Cohort X, Reference Ranges xxx - yyyy <unit>

y-axis:

range: depending on data
label: Value

x-axis:

range: Visits : Screening, D1 to D28 (depending on data) visit. Incl Early Tx DC at the end of the x-axis.

label: Visit

Box-Whisker Plots:

different styles/colors for the treatment-groups

Plots shifted to not overlap

Default SAS Box-Whisker-Plots - Min, 25%, Median, 75%, Max. Whiskers as 1.5 IQR. Mean included.

Footnotes to be used for the Box-Whisker-Plots :

Visit "Early Tx DC (TXDC)" denotes Early Treatment Discontinuation Visit. Reference Ranges do not necessarily present "values of concern" in this population but will give some context to the results relative to a normal population.

(Notes for programmer:

- replace <Parameter> <unit>, in label by actual parameter and unit used
- Adapt Visits as relevant for the different parameters. Not all parameters are reported for all visits, only scheduled visits to be included in the Figure
- display for: Hemoglobin, Platelets, Activated partial thromboplastin time (aPTT), prothrombin time (PT), Prothrombin International Normalized Ratio (INR), d-dimer, Anti-Xa, Aspartate aminotransferase (AST), Alanine aminotransferase (ALT), Total bilirubin, Creatinine, Creatinine Clearance, Estimated
- Include reference lines for each parameter in the Box-Whisker-Plot based on the table below. Use the last column "Proposed Reference Range for Boxplots".

Given that normal ranges for laboratory values vary from center to center, we propose standard reference lines be added to the boxplots based on ranges available from the American Board of Internal Medicine (January 2020). Specifically, we will implement this approach according to the ranges noted in the table below without objection. It should be noted that these ranges do not necessarily represent "values of concern" in this population but will give some context to the results relative to a normal population.

Test	ABIM Reference Range	Proposed Reference Range for Boxplots
Hemoglobin	Female: 120-160 g/L Male: 140-180 g/L	120-180 g/L
Platelets	150-450 10 ⁹ /L	150-450 10 ⁹ /L
aPTT	25-35 sec	25-35 sec
PT	11-13 sec	11-13 sec
PT-INR*	n/a	0.8-1.2
D-dimer	<0.5 mg/L	0-0.5 mg/L
Anti-Xa	0.3-0.7 IU/mL	0.3-0.7 IU/mL
AST	10-40 U/L	10-40 U/L
ALT	10-40 U/L	10-40 U/L
Total Bilirubin	5.13-17.10 umol/L	5.13-17.10 umol/L
Creatinine	Female: 44.21-97.26 umol/L Male: 61.89-114.95 umol/L	44.21-114.95 umol/L
Creatinine Clearance	90-140 mL/min/1.73m ²	90-140 mL/min

* Upper reference corresponds to lowest CTCAE Grade 1 result; lower reference from Medline

Table 17: Listing of Prior and Concomitant Medications (only Targeted Medications) - Safety Set

Subject Age/Sex/Race	Treatment Group	ATC Level 2/ Preferred Term/ Medication Name	Start Date (Study Day)	Stop Date (Study Day)	Dose [Unit]	Frequency	Route	Indication
999-999 / 70/F/W	DSTAT 0.25	ATC Level 2 Preferred Term Medication Name	DdMMMyy (xx)	DdMMMyy (xx)	40 [mg]	BID	IV	AE: xxxxxxxxxxxxxxx AE: xxxxxxxxxxxxxxx AE: xxxxxxxxxxxxxxx
999-999 / xx/xx/xx	Cohort 1 PBO	ATC Level 2 Preferred Term Medication Name	DdMMMyy (xx)	Ongoing			PBO	MH: xxxxxxxxxxxxxxx MH: xxxx
999-999 / xx/xx/xx	Cohort 1 PBO	ATC Level 2 Preferred Term Medication Name	DdMMMyy (xx)	Ongoing			PBO	PR: xxxxxxxx

Note: Medications are coded using WHO-DD Version March 2020.

Study Days prior to first treatment date are calculated as (actual date - first treatment date), after first treatment date as (actual date - first treatment date) + 1.

AE: Adverse Event, MH: Medical History, PR: Prophylaxis or Other

Page x of y

(Notes for programmer:

- Sorted by subject number, start date, stop date, ATC Level 2, preferred term and Medication Name

- Target Medications are:

Remdesvir (WHO-DC starting with "142690")
Dexamethasone (WHO-DC starting with "000160")
Anti-XA (enoxaparin) (WHO-DC starting with "017082" or "000277")

- Indication: If multiple, concatenate and wrap, drop the AE/MH-Numbers
)

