3. DERIVATIONS AND DEFINITIONS

Kaplan-Meier estimates

Time to xxx (days): Days are calculated as (start date/time – first study drug date/time)/24h). Time will be censored at last individual date/time reported.

Worst-case results in 2 scenarios for missing time-values:

1. Missing time for negative events will be imputed with “00:01”, missing time for censored observations will be imputed with “23:59”.

Negative events are:

- Time to first invasive mechanical ventilation or ECMO
- Time to first invasive mechanical ventilation, ECMO or all-cause mortality
- Time to all-cause mortality

2. Missing time for positive events will be imputed with “23:59”, missing time for censored observations will be imputed with “00:01”.

Positive events are:

- Time to clinical improvement
- Time to hospital discharge

In addition, to avoid bias in the positive events, deaths occurring prior to the positive event being observed will be censored at Day 28.

Ventilator-free days

Ventilator-free days are only counted from baseline through Day 28 or end of study, whichever comes first. They are derived based on the eCRF data collected on the Ventilator/Oxygen/Medical Care Status CRF page, Ventilator-free days are all days where Ventilator/Oxygen/Medical Care Status is not equal “Invasive Mechanical Ventilation or extracorporeal membrane oxygenation (ECMO)”.

Ventilator days are defined as cumulative rounded number of days with Ventilator/Oxygen/Medical Care Status = “Invasive Mechanical Ventilation or extracorporeal membrane oxygenation (ECMO)” divided by 24 h. Missing time for start will be imputed with “00:01”, missing time for stop will be imputed with “23:59”.

Study duration in days is defined as: Date of study completion (or date of early study discontinuation) – date of first study treatment + 1. For subjects randomized but not treated the date of randomization will be used instead of first study treatment date. The maximum study duration is set to 28 days, even if study completion or study discontinuation is after 28 days.

Ventilator-free days are defined as: study duration - number of ventilator days. For subjects who died during the course of the study, the number of ventilator-free days will be defined as 0.

Randomized, but not treated subjects:

The following rules will apply for randomized subjects without receiving study treatment, if not stated otherwise:

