Unknown/Not Answered	xx (xx.x)	xx (xx.x)	xx (xx.x)	xx (xx.x)
Death (during treatment period)	xx (xx.x)	xx (xx.x)	xx (xx.x)	xx (xx.x)

N = Number of subjects in a specific group; n = Number of subjects with data available; Percentages are based on N;

Page X of Y

(Note for programmer: Death (during treatment period) to be derived in case death date = date of last treatment start date or stop date)

Table 6: Study disposition - Randomized Subjects

Study Disposition	DSTAT 0.25 N=xxx	Cohort 1 PBO N=xxx	DSTAT 0.325 N=xxx	Cohort 2 PBO N=xxx
Primary reason for early termination				
Randomized subjects, n (%)	xx (xx.x)	xx (xx.x)	xx (xx.x)	xx (xx.x)
Randomized not treated subjects, n (%)	xx (xx.x)	xx (xx.x)	xx (xx.x)	xx (xx.x)
Treated subjects, n (%)	xx (xx.x)	xx (xx.x)	xx (xx.x)	xx (xx.x)
Completed study, n (%)	xx (xx.x)	xx (xx.x)	xx (xx.x)	xx (xx.x)
Ongoing, n (%)	xx (xx.x)	xx (xx.x)	xx (xx.x)	xx (xx.x)
Discontinued study	xx (xx.x)	xx (xx.x)	xx (xx.x)	xx (xx.x)
Primary reason for study discontinuation, n (%)				
Patient withdrawal of consent	xx (xx.x)	xx (xx.x)	xx (xx.x)	xx (xx.x)
Adverse Event	xx (xx.x)	xx (xx.x)	xx (xx.x)	xx (xx.x)
Use of a prohibited therapy	xx (xx.x)	xx (xx.x)	xx (xx.x)	xx (xx.x)
Non-compliance	xx (xx.x)	xx (xx.x)	xx (xx.x)	xx (xx.x)
Lost to follow-up	xx (xx.x)	xx (xx.x)	xx (xx.x)	xx (xx.x)
Investigator decision	xx (xx.x)	xx (xx.x)	xx (xx.x)	xx (xx.x)
Sponsor decision	xx (xx.x)	xx (xx.x)	xx (xx.x)	xx (xx.x)
Other	xx (xx.x)	xx (xx.x)	xx (xx.x)	xx (xx.x)
Unknown/Not Answered	xx (xx.x)	xx (xx.x)	xx (xx.x)	xx (xx.x)
Death, n (%)	xx (xx.x)	xx (xx.x)	xx (xx.x)	xx (xx.x)

N = Number of randomized subjects in a specific group; n = Number of subjects with data available; Percentages are based on N;

Page X of Y

Table 7: Proportion of subjects who go on invasive mechanical ventilation or ECMO - Safety Set

	DSTAT 0.25 N=xxx	Cohort 1 PBO N=xxx	DSTAT 0.325 N=xxx	Cohort 2 PBO N=xxx
Number of subjects with any invasive mechanical ventilation, ECMO or early study discontinuation, n (%) (a)	xx (xx.x)	xx (xx.x)	xx (xx.x)	xx (xx.x)
Any invasive mechanical ventilation	xx (xx.x)	xx (xx.x)	xx (xx.x)	xx (xx.x)
Early study discontinuation < Day 25	xx (xx.x)	xx (xx.x)	xx (xx.x)	xx (xx.x)
Kaplan-Meier estimates (b)				
Number of censored subjects, n (%) (b)	xx (xx.x)	xx (xx.x)	xx (xx.x)	xx (xx.x)
Time to first invasive mechanical ventilation or ECMO (days) (b)				
25% Quartile (95% CI)	x.x (x.xx,x.xx)	x.x (x.xx,x.xx)	x.x (x.xx,x.xx)	x.x (x.xx,x.xx)

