Median (95% CI)	x.x (x.xx,x.xx)	x.x (x.xx,x.xx)	x.x (x.xx,x.xx)	x.x (x.xx,x.xx)
75% Quartile (95% CI)	x.x (x.xx,x.xx)	x.x (x.xx,x.xx)	x.x (x.xx,x.xx)	x.x (x.xx,x.xx)
Number of subjects who stopped invasive mechanical ventilation or ECMO, n(%) (c)	xx (xx.x)	xx (xx.x)	xx (xx.x)	xx (xx.x)
Kaplan-Meier estimates (c)				
Number of censored subjects, n (%) (c)	xx (xx.x)	xx (xx.x)	xx (xx.x)	xx (xx.x)
Duration of first invasive mechanical ventilation or ECMO (days) (c)				
25% Quartile (95% CI)	x.x (x.xx,x.xx)	x.x (x.xx,x.xx)	x.x (x.xx,x.xx)	x.x (x.xx,x.xx)
Median (95% CI)	x.x (x.xx,x.xx)	x.x (x.xx,x.xx)	x.x (x.xx,x.xx)	x.x (x.xx,x.xx)
75% Quartile (95% CI)	x.x (x.xx,x.xx)	x.x (x.xx,x.xx)	x.x (x.xx,x.xx)	x.x (x.xx,x.xx)

N = Number of subjects in a specific group; n = Number of subjects with data available; Percentages are based on N; ECMO: Extracorporeal membrane oxygenation.

(a) Subjects with any invasive mechanical ventilation, ECMO or early study discontinuation before Day 25 will be counted as event.

(b) Kaplan-Meier estimates: Subjects with any invasive mechanical ventilation or ECMO will be counted as event. All other subjects will be censored. Time to first invasive mechanical ventilation or ECMO (days): Days are calculated as (start date/time - first study drug date/time)/24h). Time will be censored at last individual date/time reported. If time is not available for events "00:01" will be imputed, for censored observations "23:59" will be imputed.

(c) Kaplan Meier estimates: Duration of first invasive mechanical ventilation or ECMO (days): Only calculated for subjects with an invasive mechanical ventilation or ECMO reported. Duration is calculated as (stop date/time - start date/time)/24h). If start time is not available "00:01" will be imputed, if end time is missing "23:59" will be imputed. Duration will be censored for subjects with ongoing ventilation at last individual date/time reported.

Page X of Y

Figure 1: Time to first invasive mechanical ventilation or ECMO (KM-Plot) - Safety Set

Kaplan-Meier Plot:

y-axis:

range: 0% to 100% by 20%

label: Event-free Probability

reference-line: 50%

x-axis:

range: 0 to xxx (depending on data), by 7 days

label: Time to Event (Days)

Lines:

solid

different colors/line styles for the treatment-groups

starting at (100%/Baseline)

Censored values marked

Please use the following footnote for Figure 1 :

N = Number of subjects in a specific group; (+) = censored values;

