Kaplan-Meier estimates: Subjects with any invasive mechanical ventilation or ECMO will be counted as event. All other subjects will be censored.

Time to first invasive mechanical ventilation or ECMO (days): Days are calculated as (start date/time - first study drug date/time)/24h). Time will be censored at last individual date/time reported. If time is not available for events "00:01" will be imputed, for censored observations "23:59" will be imputed.

Figure 2: Duration of first invasive mechanical ventilation or ECMO (KM-Plot) - Safety Set

Kaplan-Meier Plot:

y-axis:

range: 0% to 100% by 20%
label: Event Probability
reference-line: 50%

x-axis:

range: 0 to xxx (depending on data), by 7 days
label: Duration (Days)

Lines:

solid
different colors/line styles for the treatment-groups
starting at (0%/Baseline)
Censored values marked

Please use the following footnote for Figure 2 :

N = Number of subjects in a specific group; (+) = censored values;

Kaplan Meier estimates: Duration of first invasive mechanical ventilation or ECMO (days): Only calculated for subjects with an invasive mechanical ventilation or ECMO reported. Duration is calculated as (stop date/time - start date/time)/24h. If start time is not available "00:01" will be imputed, if end time is missing, "23:59" will be imputed. Duration will be censored for subjects with ongoing ventilation at last individual date/time reported.

Table 8: Treatment-emergent Adverse Events (TEAEs) - Safety Set

Primary system organ class Preferred term	DSTAT 0.25 N=xxx n (%)	Cohort 1 PBO N=xxx n (%)	DSTAT 0.325 N=xxx n (%)	Cohort 2 PBO N=xxx n (%)
Number (%) of subjects with at least one such AE	xx (xx.x)	xx (xx.x)	xx (xx.x)	xx (xx.x)
SOC 1	xx (xx.x)	xx (xx.x)	xx (xx.x)	xx (xx.x)
PT 1	xx (xx.x)	xx (xx.x)	xx (xx.x)	xx (xx.x)
PT 2	xx (xx.x)	xx (xx.x)	xx (xx.x)	xx (xx.x)
:	xx (xx.x)	xx (xx.x)	xx (xx.x)	xx (xx.x)
SOC 2	xx (xx.x)	xx (xx.x)	xx (xx.x)	xx (xx.x)
:	xx (xx.x)	xx (xx.x)	xx (xx.x)	xx (xx.x)

N = Number of subjects in a specific group; n = Number of subjects with at least one event in the category;

Percentages are based on N; Adverse events are coded using MedDRA version 23.0.

If a subject has multiple occurrences of an AE, the subject is presented only once in the respective subject count (n).

Page X of Y

(Note for programmer: AEs are sorted by descending patients' frequency of SOC and by descending frequency of PT within the SOC in the DSTAT 0.25)

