(a) Subjects with a clinical improvement will be counted as event.

(b) Kaplan-Meier estimates: Subjects with a clinical improvement will be counted as event. Subjects without a clinical improvement or deaths occurring prior to the positive event will be censored. Time to clinical improvement: Days are calculated as (start date/time - first study drug date/time)/24h. Time will be censored at last individual date/time reported. If time is not available for events "23:59" will be imputed, for censored observations "00:01" will be imputed. Participants who died prior to Day 28 without clinical improvement will be censored at Day 28. Randomized untreated subjects will be censored at time = 0.

Page X of Y

(Notes for programmer: Subjects randomized not treated will be counted as censored observation (censor time = 0)
)

Figure 7: Time to clinical improvement (KM-Plot) - ITT Set

Kaplan-Meier Plot:

y-axis:

range: 0% to 100% by 20%
label: Event Probability
reference-line: 50%

x-axis:

range: 0 to xxx (depending on data), by 7 days
label: Time to Event (Days)

Lines:

solid
different colors/line styles for the treatment-groups
starting at (0%/Baseline)
Censored values marked

Footnote:

N = Number of subjects in a specific group; (+) = censored values;

Clinical improvement is defined as at least a 2-grade improvement from baseline on the NIAID ordinal score.

Kaplan-Meier estimates: Subjects with a clinical improvement will be counted as event. Subjects without a clinical improvement or deaths occurring prior to the positive event will be censored.

Time to clinical improvement (days): Days are calculated as (start date/time - first study drug date/time)/24h). Time will be censored at last individual date/time reported. If time is not available for events "23:59" will be imputed, for censored observations "00:01" will be imputed. Participants who died prior to Day 28 without clinical improvement will be censored at Day 28. Randomized untreated subjects will be censored at time = 0.

(Notes for programmer: Subjects randomized not treated will be counted as censored observation (censor time = 0)

)

Table 23: Number of ventilator-free days from baseline through Day 28 - ITT Set

	DSTAT 0.25 N=xxx	Cohort 1 PBO N=xxx	DSTAT 0.325 N=xxx	Cohort 2 PBO N=xxx
Number of ventilator-free days, n(%)				
0	xx (xx.x)	xx (xx.x)	xx (xx.x)	xx (xx.x)
1	xx (xx.x)	xx (xx.x)	xx (xx.x)	xx (xx.x)
2	xx (xx.x)	xx (xx.x)	xx (xx.x)	xx (xx.x)
3	xx (xx.x)	xx (xx.x)	xx (xx.x)	xx (xx.x)

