4	xx (xx.x)	xx (xx.x)	xx (xx.x)	xx (xx.x)
5	xx (xx.x)	xx (xx.x)	xx (xx.x)	xx (xx.x)
6	xx (xx.x)	xx (xx.x)	xx (xx.x)	xx (xx.x)
7	xx (xx.x)	xx (xx.x)	xx (xx.x)	xx (xx.x)
8	xx (xx.x)	xx (xx.x)	xx (xx.x)	xx (xx.x)
...				
28	xx (xx.x)	xx (xx.x)	xx (xx.x)	xx (xx.x)
n	xxx	xxx	xxx	xxx
Mean	xx.x	xx.x	xx.x	xx.x
SD	xx.x	xx.x	xx.x	xx.x
Median	xx	xx	xx	xx
Q1, Q3	xx, xx	xx, xx	xx, xx	xx, xx
Min, Max	xx, xx	xx, xx	xx, xx	xx, xx

N = Number of subjects in a specific group; n = Number of subjects with data available; Percentages are based on N; SD: Standard deviation; Q1, Q3: First, third quartile; Min: minimum; Max: maximum.

Ventilator-free days are only counted through the date of early study discontinuation, study completion date or Day 28, whichever comes first. For subjects who die during the course of the study, number of ventilator-free days is defined as 0.

Page X of Y

(Notes for programmer:

Include only the categories of Days (0-28) in the table which are available in the data
)

Table 24: Time to last hospital discharge - ITT Set

	DSTAT 0.25 N=xxx	Cohort 1 PBO N=xxx	DSTAT 0.325 N=xxx	Cohort 2 PBO N=xxx
Number of subjects discharged from hospital, n (%) (a)	xx (xx.x)	xx (xx.x)	xx (xx.x)	xx (xx.x)
Kaplan-Meier estimates (b)				
Number of censored subjects, n (%) (b)	xx (xx.x)	xx (xx.x)	xx (xx.x)	xx (xx.x)
Number of subjects alive and still in hospital	xx (xx.x)	xx (xx.x)	xx (xx.x)	xx (xx.x)
Death	xx (xx.x)	xx (xx.x)	xx (xx.x)	xx (xx.x)
Time to hospital discharge (days) (b)				
25% Quartile (95% CI)	x.x (x.xx, x.xx)	x.x (x.xx, x.xx)	x.x (x.xx, x.xx)	x.x (x.xx, x.xx)
Median (95% CI)	x.x (x.xx, x.xx)	x.x (x.xx, x.xx)	x.x (x.xx, x.xx)	x.x (x.xx, x.xx)
75% Quartile (95% CI)	x.x (x.xx, x.xx)	x.x (x.xx, x.xx)	x.x (x.xx, x.xx)	x.x (x.xx, x.xx)

N = Number of subjects in a specific group; n = Number of subjects with data available; Percentages are based on N;
 (a) Subjects discharged from hospital will be counted as event.

(b) Kaplan-Meier estimates: Subjects discharged from hospital will be counted as event. Subjects who are still in the hospital or died in the hospital will be censored.

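### SAP Table 7 footnote (c) and Figure 2 give no rule for death during the first ventilation or ECMO episode, so the duration curve can overstate coming off support

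*SAP*

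**What the plan says.** Table 7 (SAP 5.1) has a row "Number of subjects who stopped invasive mechanical ventilation or ECMO, n(%) (c", followed by a censored count and Kaplan-Meier quartiles for the duration of the first episode. Footnote (c) restricts the calculation to subjects with ventilation or ECMO reported and takes duration as stop minus start. Its censoring rule is "Duration will be censored for subjects with ongoing ventilation at last individual date/time reported". The same text sits under "Figure 2: Duration of first invasive mechanical ventilation or ECMO (KM-Plot) - Safety Set". Neither place mentions death, and the row is not split by vital status. Percentages use the whole arm as denominator: "Percentages are based on N; ECMO: Extracorporeal membrane oxygenation".

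Elsewhere the SAP does say what happens to deaths:

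- Section 3: "In addition, to avoid bias in the positive events, deaths occurring prior to the positive event being observed will be censored at Day 28". The positive events it lists are time to clinical improvement and time to hospital discharge; ventilation duration is not among them.
- Table 22: "Participants who died prior to Day 28 without clinical improvement will be censored at Day 28". Table 24: "Subjects who are still in the hospital or died in the hospital will be censored". Both carry a separate Death row among the censored.
- Tables 18 and 19 count death as an event.
- Section 3 and Table 23 set ventilator-free days to 0 for anyone who dies.

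Protocol Table 1, footnote e, asks for date and time of ventilation start and stop and of death as separate items. It does not say whether a stop is entered when a subject dies on the ventilator.

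**The concern.** Death on the ventilator rules out coming off it alive; it does not merely hide when that would have happened. The footnote leaves two ways to program such a death:

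1. The ventilation record is open at death. The only rule that fits is the one for ongoing ventilation, so the subject is censored at last contact. Kaplan-Meier then assumes that this subject would have stopped later at the same rate as those still ventilated.
2. A stop has been entered at death. The subject then counts as having stopped, and the time of death ends the duration.

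Under the first, the curve and quartiles can show more or earlier liberation than occurred. Under the second, the count is affected as well, and an arm in which every ventilated subject died would look the same as one in which every ventilated subject was weaned on those days. The table belongs to the DMC package, and the sponsor may also unblind and review it after Cohort 1 and/or 2. In arms this small, one or two deaths determine what it shows.

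**Working it through.** The plan states no figure for ventilation duration, so there is none to reproduce. The check has two parts.

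**1. What each reading prints.** At each time t let n be the number still at risk, s the stops alive and d the deaths on support.

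- Deaths censored: 1 − KM, where KM is the product of (1 − s/n).
- Deaths as stops: the same with (1 − (s+d)/n).
- Cumulative incidence of stopping alive: the sum of S(t−)·s/n, where S is the product of (1 − (s+d)/n).

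Invented data, times in days from start of ventilation:

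| Ventilated subjects | Deaths censored | Deaths as stops | Cumulative incidence |
|---|---|---|---|
| Death 4, weaned 10 | 1/2 stopped; 100% off by day 10 | 2/2 stopped | 50% off alive, 50% dead |
| Deaths 3 and 4, weaned 10 | 1/3 stopped; median 10; 100% off by day 10 | 3/3 stopped; median 4 | 33% off alive, 67% dead |
| Weaned 6, death 10, weaned 14 | 2/3 stopped; median 14; 100% off by day 14 | 3/3 stopped; median 10 | 67% off alive, 33% dead |
| Death 4 only | 0/1 stopped; median not reached | 1/1 stopped; median 4 | 0% off alive |

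First row in full. Deaths censored: at day 10 one subject is at risk and stops, so 1 − (1 − 1/1) = 100%. Cumulative incidence: S falls to 1 − 1/2 = 0.5 at day 4, and at day 10 the increment is 0.5 × 1/1 = 0.5.

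The first column's count is right in every row. Its curve is wrong only where a weaning comes after a death; in the last row, with no weaning, nothing is distorted. In an arm of 6, the second row's count would print as 1 (16.7%) or 3 (50.0%).

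**2. How often this can arise.** Inputs: arms of 6 and 6 in Cohort 1 and 8 and 4 in Cohort 2 (Protocol 4.1), and the planning failure rates of 9% and 20% (Protocol 9.2). Those rates include death without ventilation, so I use them as an assumed upper bound on p, the chance of being ventilated. The share of ventilated subjects who die on support is not given; I assume one half, in exchangeable order.

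With k ventilated, the curve is undistorted only if all weanings precede all deaths, which has probability (k+1)/2^k. Averaging over k ~ Binomial(n, p), and writing q = p/2:

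P(a weaning follows a death) = 1 − (1−q)^n − nq(1−q)^(n−1).

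For n = 6 and p = 0.20: 1 − 0.9^6 − 0.6 × 0.9^5 = 1 − 0.531 − 0.354 = 0.114.

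| Arm size | Weaning follows a death (censored curve wrong) | At least one death on support, 1 − (1−q)^n |
|---|---|---|
| 4 | 1.1–5.2% | 16.8–34.4% |
| 6 | 2.7–11.4% | 24.1–46.9% |
| 8 | 4.7–18.7% | 30.8–57.0% |

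A share of one half maximizes the middle column. With a share of one quarter or three quarters it becomes 0.9–3.9%, 2.0–8.6% and 3.6–14.1%, from 1 − 1.5(1 − p/4)^n + 0.5(1 − 3p/4)^n. The last column does depend on the share: in an arm of 6 it is 12.8–26.5% at one quarter and 34.3–62.3% at three quarters, from 1 − (1 − p × share)^n. It matters only if sites enter a stop at death.

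**The case against.** The strongest reply is that Table 7(c) is a small descriptive display whose rows speak of stopping and duration, not of weaning. Ventilation duration is not a protocol endpoint. The protocol's own measure of time on support, ventilator-free days, gives deaths a value of 0, and Tables 18 and 19 count death explicitly. Deaths are also visible in Tables 2, 6 and 12, and the plot marks censored subjects. All of this stands and limits the weight of the point. None of it alters the numbers that Table 7(c) and Figure 2 would print.

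Four stronger readings are tempting and should be resisted.

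- A reader might infer that the stopped count is wrong as written. With an open record it is right; it fails only if a stop is entered at death, and the eCRF coding is not shown.
- The Table 5 note, "Death (during treatment period) to be derived in case death date = date of last treatment start date or stop date", might be taken as evidence of such coding. It concerns study-drug dates and says nothing about ventilation records.
- The chance that an arm has any ventilated subject (43–74% for n = 6 at the planning rates) might be read as the chance of distortion. Distortion of the censored curve needs a weaning after a death in the same arm, which is far less common.
- Protocol 9.4.2 promises that the SAP will deal with deaths for each time-to-event secondary endpoint. Ventilation duration is not one of them, so its absence here does not breach that promise.

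It is also fair to say that a change of estimator adds little with up to about three ventilated subjects in an arm. A plain listing with outcomes is an acceptable alternative.

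**Conclusion.** The gap is real and its effect is minor. No passage supplies a rule for death during the first episode. Read literally, the footnote censors such a death, and the curve and quartiles then overstate coming off support whenever a weaning follows it in the same arm. At one half dying on support, and with the planning rates as an upper bound for ventilation, that happens in about 1% to 19% of arms, depending on arm size. The error can be large when it does happen (100% shown against 33% or 50% in the examples). The miscount of stops is conditional on a coding practice that the documents do not show.

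The documents do not support extending this to the primary endpoint, the key secondary endpoint or Phase 3: the output carries no test, Cohorts 1 and 2 are described only, and Phase 2 data are kept out of the confirmatory inference (Protocol 9.4).

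**What to change.** 1. In footnote (c) and under Figure 2, state that death during the first ventilation or ECMO episode is not a stop, whether that record is open at death or its recorded stop is the death itself. Compare date and time where both exist. Flag same-date cases with a missing time for review, because a missing stop time is set to 23:59 and can fall after the death.
2. Split the row into: stopped first episode alive; died during first episode; still on support at last contact. Tie all three to the first episode, so that a later re-ventilation and death does not reclassify an earlier weaning.
3. For the duration, show the cumulative incidence of coming off the first episode alive, with death on support as the competing event and only living subjects still on support censored. Given the numbers, a listing of individual durations with outcome would also do. Do not keep Kaplan-Meier with deaths censored.
4. Do not borrow the Day 28 device from Section 3. Its clock starts at first dose and this one starts at ventilation. It also gives a different answer once someone is still ventilated at last contact. With a death at 3 days, ongoing support censored at 8 and weaning at 10, holding the death in the risk set gives 1/2 = 50% off at day 10; the cumulative incidence is (2/3) × 1/1 = 67%.
5. Make the same change in the DMC version of Table 7 and Figure 2, or note the difference, because SAP Section 2 says that the two outputs will be equivalent.

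The cost is a sentence, a row split and a little programming, with dates that the protocol already collects. Quartiles may not be reached, and a weaning and a death on the same day may be misclassified.
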